7.3.2 Administration

The patient and their carer/s will be instructed in the correct use of the medications dispensed. Patients will be instructed in the proper use and care of their inhaler by the RN at T-4 and will have their technique assessed. Further guidance will be provided throughout the remainder of the trial where necessary.

The trial treatments have two different routes of administration:

1. inhalation (fluticasone/salmeterol)

One inhalation to be taken twice daily at regular intervals (e.g. once in the morning and once in the evening).

2. oral (montelukast/placebo)

One tablet is to be administered daily, to be taken in the evening. If taken in conjunction with food, montelukast should be taken one hour before or two hours after eating.

7.4 Dose Modifications

The decision to interrupt or discontinue trial therapy is at the discretion of the treating physician. Doses may be interrupted or discontinued at any point during the trial period for reasons such as unacceptable adverse effects, intercurrent illness, development of serious disease or any change in the patient's condition that the physician believes warrants a change in medication (see Section 5.3.2). Any changes must be documented in the CRF along with the justification for those changes.

7.5 Accountability Procedures for Study Treatment/s

Clinical trial supplies will only be delivered to an investigator site once the site has been initiated. This can only be completed once full ethical and regulatory approvals have been granted. This must be confirmed by

the Trial Coordinator acting on behalf of the study sponsor. The size of the shipments to each site will be pre-determined based on the patient recruitment target for that individual site. The first shipment will be approximately a quarter of the total trial supplies for the site and there will be a maximum of three subsequent shipments over the two year trial period. Recruitment will be monitored centrally and drug shipment dates will be tailored accordingly to ensure that pharmacies always hold adequate supplies of trial treatment. Pharmacies will document all shipment receipts and will provide copies of this documentation to the Trial Coordinator.

Following registration into the trial of an individual participant, the following accountability procedures for clinical trial supplies at pharmacy will apply:

At T-4 the RN/PI will collect an inhaler of fluticasone propionate (open label) from pharmacy and record the receipt of this by the patient on the T-4 CRF. Pharmacy will put their dispensing label (including information such as patient name or initials, pharmacy address, telephone number and date of dispensing) on to the inhaler carton and will complete, sign and date the accountability log. A second member of the pharmacy team will counter-sign the log to document the dispensing.

At T0 the patient will be randomised and a blinded treatment pack will be dispensed by pharmacy according to their treatment allocation. Pharmacy will ensure that the participant and the researcher remain blinded to the treatment allocation. Pharmacy will put their dispensing label (including information such as patient name or initials, pharmacy address, telephone number and date of dispensing) on to the pack and will complete, sign and date the accountability log. A second member of the pharmacy team will counter-sign and date the log to document the dispensing. The RN will record the participant's randomisation number in the CRF. Upon allocation, the patient's trial number will also be recorded in their individual hand held asthma record.

At each subsequent dispensing, the patient's randomised treatment allocation will be ascertained by pharmacy and a treatment pack/s dispensed on production of a valid trial prescription. Pharmacy will ensure that the participant and the researcher remain blinded to the treatment allocation. The accountability log will be updated and signed and dated by two members of the pharmacy team. Where the prescription is dispensed to the RN for transport to another site, the RN will transport the medications securely ensuring that the temperature of the products is controlled and recorded. At all study visits from T0-T+48, unused medications (including omitted doses from the previous prescription's regimen) will be collected by the RN and returned to pharmacy for destruction.

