7.3 Preparation, Dosage and Administration of Study Treatment/s

7.3.1 Dispensing

For each randomised patient, treatment will continue for a maximum period of 48 weeks. Patients will be randomised by pharmacy using a randomisation list provided to the site by the coordinating centre. Pharmacy will ensure that the participant and the researcher are blinded to the treatment allocation. After

randomisation patients will be dispensed their first treatment pack. Each treatment pack contains three months of trial medication, consisting of:

- Three inhalers (each inhaler containing 60 inhalations or 30 days treatment)
- Three blister packs (each blister pack containing 35 days treatment)

All treatments will be dispensed at the standard dose throughout the trial, unless interruption or discontinuation is warranted and agreed by the PI (see Section 7.4). The dose regimens are:

A. inhaled fluticasone propionate 100micrograms twice daily + placebo tablet once daily

B. inhaled fluticasone propionate 100micrograms and salmeterol 50micrograms twice daily (combination inhaler) + placebo tablet once daily

C. inhaled fluticasone propionate 100micrograms twice daily + montelukast 5mg tablet once daily.

When pharmacy dispense the trial treatments they will add their own dispensing label, which will include information such as the name and address of the hospital, the patient's name or initials, date of dispensing and instructions for use. They will also complete the information specified on the medication trial labels (i.e. patient trial number, visit number etc.).

The medications will be dispensed upon production of a valid, signed trial prescription to either the RN or directly to the patient and their carer/s as detailed below*:

T-4 study visit

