One inhaler of fluticasone propionate (open label) will be dispensed for a registered participant at T-4 on receipt of a valid trial prescription. If the T-4 visit is conducted at an outreach or community site (e.g. a GP practice) and the participant is registered during the visit the RN will arrange for them to receive the study medication once it has been dispensed from pharmacy. The dispensed medication will be collected from pharmacy and securely transported by a member of the research team, ensuring temperature monitoring is conducted until it is given to the patient. The RN will arrange with the patient and their carer/s to collect the medication from the outreach site, ensuring that it is collected by the family within an agreed timeframe (no longer than three days).

T0 study visit

The participant will be randomised to a treatment arm by pharmacy. Ensuring the RN and participant remain blinded as to the treatment allocation, one three month treatment pack containing three inhalers and three monthly blister cards will be dispensed on receipt of a valid trial prescription. If the T0 visit is conducted at an outreach or community site (e.g. a GP practice) and the participant is randomised during the visit the RN will arrange for them to receive the study medication once it has been dispensed from pharmacy. The dispensed medication will be collected from pharmacy and securely transported by a member of the research team, ensuring temperature monitoring is conducted until it is given to the patient. The RN will arrange with the patient and their carer/s to collect the medication from the outreach site, ensuring that it is collected by the family before the patient runs out of their current prescription.

T+8 study visit

The participant's randomised treatment allocation will be ascertained by pharmacy. Ensuring the RN and participant remain blinded as to the treatment allocation, one three month treatment pack containing three inhalers and three monthly blister cards will be dispensed from pharmacy on receipt of a valid trial prescription.

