7.6 Assessment of Compliance with Study Treatment/s

Participants will be asked to retain all used and unused trial medications and packaging and bring them to each study visit from T0–T+48. The research doctor/nurse will collect the returned supplies in order to assess compliance with the trial treatment regimen. The inhalers supplied to the participants contain dose counters which show the number of doses remaining. Once the compliance checks have been completed and recorded, the RN will deliver all returned medications to pharmacy for destruction via their local procedures.

T0 study visit

All registered participants will be asked to bring the fluticasone inhaler they were issued at T-4 to the T0 study visit. The research doctor/nurse will ask the participant and their carer/s about compliance with the treatment regime and whether any doses have been missed. At the end of the study visit, after the patient has left, the researcher will use the dose counter on the inhaler to verify the information provided by the family. The number of inhalations reported by both the participant and the dose counter will be recorded on the CRF along with the reason given for any doses missed (if applicable).

T+8 study visit

The research nurse will collect all used medications and packaging from the participant. The participant will have been issued with 12 weeks of treatment at T0 so will retain one inhaler and one monthly blister pack for use over the next four weeks.

The research nurse will ask the participant and their carer/s about compliance with the treatment regime since their last visit and whether any inhalations or tablets have been missed. At the end of the study visit, after the patient has left, the researcher will use the dose counter on the inhaler and conduct a full pill count to verify the information provided by the family. The number of doses reported by the participant and from the medication counts will be recorded on the CRF along with the reason given for any doses missed (if applicable).

T+24 study visit

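### Protocol 7.5 and the Norfolk dispensing procedure take back unused trial medication at T+8, but the T+8 paragraph of 7.6 relies on one inhaler and one blister pack being kept; without them the supply to T+24 is about 22 inhaler days short

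*Protocol*

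**What the plan says.** The protocol describes take-back of trial medication in four places.

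- **Section 7.5 (accountability).** The rule covers every visit and makes no exception for T+8: "At all study visits from T0-T+48, unused medications", omitted doses among them, are taken back by the nurse and go to pharmacy to be destroyed.
- **Section 7.6, opening.** Families bring used and unused items to each visit from T0. After the compliance check, "the RN will deliver all returned medications to pharmacy for destruction via their local procedures". No T+8 exception is stated here either.
- **Section 7.6, T+8 paragraph.** "The research nurse will collect all used medications and packaging from the participant". The reason for leaving some supply behind is then given: "The participant will have been issued with 12 weeks of treatment at T0", and the child "so will retain one inhaler and one monthly blister pack for use over the next four weeks". The paragraphs for T+24, T+48 and early withdrawal have both used and unused items collected.
- **Appendix B (Norfolk & Norwich), T+8 onwards.** The nurse collects previously dispensed medication, used or unused, and returns it to the hospital pharmacy for destruction.

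On quantities, section 7.3.1 defines a treatment pack as "Three inhalers (each inhaler containing 60 inhalations or 30 days treatment") plus three blister packs of 35 days each. At T+8, "one three month treatment pack containing three inhalers and three monthly blister cards will be dispensed from pharmacy". At T+24 two packs are dispensed. Section 8.1 puts 16 weeks between the two visits.

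**The concern.** The instructions differ on whether an unopened inhaler and an unopened blister pack go back to pharmacy or stay with the child at T+8. The quantity dispensed at T+8 is enough only under one of them. A site that applies 7.5 or Appendix B as written would be following the protocol and would still run the child out of trial medication before T+24.

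The children concerned were randomised because their asthma was uncontrolled on low-dose inhaled steroid. In all three arms the trial inhaler carries that steroid, and in arm B it also carries salmeterol. Section 7.7.2 does not permit other inhaled steroids, long-acting beta agonists or leukotriene antagonists during the trial. The primary outcome counts exacerbations treated with oral steroids over 48 weeks, so weeks without trial inhaler fall inside the outcome period. Whether those weeks occur would depend on which section a site works from.

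**Working it through.** **Inputs**

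- Inhaler: 60 inhalations, two a day (7.3.1, 7.3.2), so 60 / 2 = 30 days. Three per pack: 3 x 30 = 90 days.
- Tablets: 35 days per blister pack (7.3.1). Three per pack: 3 x 35 = 105 days.
- T+8 to T+24: 16 weeks (8.1), so 16 x 7 = 112 days.
- Visit window: where possible, no more than one week early (8.1).
- Assumptions: every dose is taken and each pack starts on the day it is dispensed.

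**The protocol's own supply logic at T+8.** 12 weeks issued minus 8 weeks elapsed leaves 4 weeks. One inhaler lasts 30 / 7 = 4.3 weeks and one blister pack lasts 35 / 7 = 5 weeks, so the statement in 7.6 reproduces.

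**Collection rule followed at T+8 (7.5, Appendix B).** The child leaves with the new pack only. Gap = days needed minus days held.

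| T+8 visit | T+24 visit | Days needed | Inhaler gap | Tablet gap |
|---|---|---|---|---|
| on time | on time | 112 | 112 - 90 = 22 | 112 - 105 = 7 |
| 1 week early | on time | 119 | 119 - 90 = 29 | 119 - 105 = 14 |
| on time | 1 week early | 105 | 105 - 90 = 15 | 105 - 105 = 0 |
| 1 week early | 1 week early | 112 | 22 | 7 |

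**One inhaler and one blister pack kept (T+8 paragraph of 7.6).**

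- Inhaler: 30 + 90 = 120 days; 120 - 112 = 8 spare.
- Tablets: 35 + 105 = 140 days; 140 - 112 = 28 spare.
- With T+8 a week early and T+24 on time: 120 - 119 = 1 inhaler day and 140 - 119 = 21 tablet days spare.

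**Is the problem wider than this interval?** From T+24 to T+48 is 24 x 7 = 168 days. Two packs give 180 inhaler days and 210 tablet days, so that period is covered. The shortfall is confined to T+8 to T+24, the interval in which the instructions disagree.

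**Scale against the outcome period.** 48 weeks is 336 days, and 22 / 336 = 6.5% of it, for a child at a site that applies the collection rule.

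**The case against.** The strongest reply is that the T+8 paragraph of 7.6 is specific and deliberate. It speaks of used items only, gives its reason, and changes to used and unused from T+24. A visit-specific instruction usually overrides a general sentence, and the dispensing quantities are sufficient only under that paragraph. One can also read unused in 7.5 as leftover doses, and the destruction sentence opening 7.6 covers returned items, which a retained inhaler is not.

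Much of this stands. The opening of 7.6 need not conflict, and a careful nurse may well leave the supply with the child. Two points remain. Section 7.5 brings in missed doses with the word including, so they are only part of what it covers, and an unopened inhaler is unused on any ordinary reading. Appendix B is itself specific: its instruction is headed for T+8 onwards and names unused medication, so the specific-over-general argument does not dispose of it.

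There are also safeguards. Section 8.1 asks teams to check remaining supply when a visit is planned late. Section 7.3.1 tells families with nothing left after loss or damage to call the nurse. Sections 7.4 and 11.2 leave the clinician free to change treatment. These make a long unnoticed gap less likely, but they are written for late visits, lost packs and clinical need, and this shortfall arises on schedule.

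The compliance point is weaker than the supply point. On scheduled dates the retained items are unopened, so a count of what is collected can still be adequate.

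**Conclusion.** The contradiction is real and should be corrected. On scheduled dates with full adherence, the collection rule leaves 22 inhaler days and 7 tablet days uncovered before T+24 (15 to 29 and 0 to 14 days across the one-week-early window). Retention of one inhaler and one blister pack leaves 8 and 28 days spare. Missed doses would shorten the gap; a late T+24 visit would lengthen it.

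Four stronger readings are tempting, and the protocol does not support them.

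- **That 22 days is the maximum.** It is the scheduled-date value, and an early T+8 visit alone gives 29.
- **That retention gives a 12-day margin**, from six inhalers or 180 days against 168. That sum includes the 60 - 56 = 4 days left in the part-used second inhaler at T+8, which is not the one kept.
- **That children will go untreated, because staff sign against 7.5.** The signatures described there are those of two pharmacy staff documenting dispensing, and the T+8 paragraph may be the one that is followed.
- **That the comparison of arms is biased.** The collection rule is the same in all three arms, randomisation is stratified by centre and the primary model adjusts for centre. What can be claimed is treatment interruption that depends on site and possible dilution of the treatment contrast. Its size cannot be given, because the number of sites that would apply each rule is unknown.

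**What to change.** Reconcile section 7.5, the opening and T+8 paragraph of 7.6, and the T+8 onwards text of Appendix B with the T+8 dispensing quantity in 7.3.1. A single rule should state which items are collected at T+8 and which stay with the child, and the other places should refer to it. Whichever rule the sponsor chooses, check days held after T+8 against 112 days, and against 119 for an early T+8 visit.

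Make the T+8 dose-counter reading and pill count consistent with that rule. As 7.6 stands, the count is done after the family has left, so the text should say whether it covers collected items only and how retained items are recorded.

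The cost is a short text edit in the places named, issued to sites. Sample size, visit schedule and analysis do not change.

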7.6 Assessment of Compliance with Study Treatment/s

Participants will be asked to retain all used and unused trial medications and packaging and bring them to each study visit from T0–T+48. The research doctor/nurse will collect the returned supplies in order to assess compliance with the trial treatment regimen. The inhalers supplied to the participants contain dose counters which show the number of doses remaining. Once the compliance checks have been completed and recorded, the RN will deliver all returned medications to pharmacy for destruction via their local procedures.

T0 study visit

All registered participants will be asked to bring the fluticasone inhaler they were issued at T-4 to the T0 study visit. The research doctor/nurse will ask the participant and their carer/s about compliance with the treatment regime and whether any doses have been missed. At the end of the study visit, after the patient has left, the researcher will use the dose counter on the inhaler to verify the information provided by the family. The number of inhalations reported by both the participant and the dose counter will be recorded on the CRF along with the reason given for any doses missed (if applicable).

T+8 study visit

The research nurse will collect all used medications and packaging from the participant. The participant will have been issued with 12 weeks of treatment at T0 so will retain one inhaler and one monthly blister pack for use over the next four weeks.

The research nurse will ask the participant and their carer/s about compliance with the treatment regime since their last visit and whether any inhalations or tablets have been missed. At the end of the study visit, after the patient has left, the researcher will use the dose counter on the inhaler and conduct a full pill count to verify the information provided by the family. The number of doses reported by the participant and from the medication counts will be recorded on the CRF along with the reason given for any doses missed (if applicable).

T+24 study visit

The research nurse will collect all used and unused medications and packaging from the participant. They will ask the participant and their carer/s about compliance with the treatment regime since their last visit and whether any inhalations or tablets have been missed. At the end of the study visit, after the patient has left, the researcher will use the dose counter on the inhaler and conduct a full pill count to verify the information provided by the family. The number of doses reported by the participant and from the medication counts will be recorded on the CRF along with the reason given for any doses missed (if applicable).

T+36 telephone call

The research nurse will ask the participant and/or their carer/s about compliance with the treatment regime since their last visit and whether any inhalations or tablets have been missed. The number of doses reported by the participant will be recorded on the CRF along with the reason given for any doses missed (if applicable). The RN will remind the participant to bring all used and unused medications and packaging to their next study visit.

T+48 study visit

The research nurse will collect all used and unused medications and packaging from the participant. They will ask the participant and their carer/s about compliance with the treatment regime since their last visit and whether any inhalations or tablets have been missed. At the end of the study visit, after the patient has left, the researcher will use the dose counter on the inhaler and conduct a full pill count to verify the information provided by the family. The number of doses reported by the participant and from the medication counts will be recorded on the CRF along with the reason given for any doses missed (if applicable).

Early withdrawal

If a patient wishes to prematurely withdraw from trial treatment, the research nurse will collect all used and unused medications and packaging from the participant. They will ask the participant and their carer/s about compliance with the treatment regime since their last visit and whether any inhalations or tablets have been missed. The researcher will use the dose counter on the inhaler and conduct a full pill count to verify the information provided by the family. The number of doses reported by the participant and from the medication counts will be recorded on the CRF along with the reason given for any doses missed (if applicable).

7.7 Concomitant Medications/Treatments

7.7.1 Medications Permitted

Details of concomitant medications will be collected at the T-4 visit and recorded on the CRF. They will be reviewed at all subsequent study visits (clinic visits, telephone call) until T+48. The trial treatments have very few adverse interactions with other medicinal products so concomitant medications, with the exception of those listed in Section 7.7.2, are permissible at the discretion of the investigator.

7.7.2 Medications Not Permitted/Precautions Required

The following are not permitted for the duration of the trial period:

- Inhaled corticosteroids (other than the trial treatment)
- Long-acting beta₂ agonists (other than trial treatment)
- Leukotriene receptor antagonists (other than trial treatment)
- All beta-blockers
- Theophylline

Caution should be exercised when prescribing CYP3A inhibitors as they may affect the efficacy of montelukast (see Singulair SPC Section 4.5 ‘Interactions with other medicinal products and other forms of interaction’). CYP3A inhibitors (e.g. ketaconazole, itraconazole) are not permitted for regular or frequent use during the trial treatment period. All prescribed CYP3A inhibitors should be documented on the Concomitant Medications CRF.

